5.5.1 Treatment Satisfaction

Treatment satisfaction related to PERTs will be measured with the Treatment Satisfaction Questionnaire for Medication – 9 items (TSQM-9). The TSQM-9 is a global satisfaction scale used to assess the overall level of participant's satisfaction or dissatisfaction with their medications. It comprises 9 items on 3 subscales: effectiveness, convenience, and global satisfaction. The scores are computed by adding items for each domain, i.e., items 1 – 3 for effectiveness, items 4 – 6 for convenience and items 7 – 9 for global satisfaction [1]. The lowest possible score (1 for each item and 3 for all 3 subscales) is subtracted from the composite score and divided by the greatest possible score range. The greatest range is $(7-1) * 3$ items = 18 for the effectiveness and convenience, and 14 for global satisfaction. This provides a transformed score between 0 and 1 that is then multiplied by 100; scores for the domains range from 0 (extremely dissatisfied) to 100 (extremely satisfied), with higher scores indicating greater satisfaction.

Table 2 Algorithm for Transforming TSQM-9 Composite Score [3]

Subscale	Algorithm	Handle missing score
Global Satisfaction	$([\text{Sum}(Item\ 7\ \text{to}\ Item\ 9) - 3] \text{ divided by } 14) * 100$	If either Item 7 or 8 is missing $([\text{Sum}(\text{the two completed items}) - 2] \text{ divided by } 10) * 100$; If Item 9 is missing $([\text{Sum}(Item7\ \text{and}\ Item8)) - 2] \text{ divided by } 8) * 100$
Effectiveness	$([\text{Item}\ 1 + \text{Item}\ 2 + \text{Item}\ 3) - 3] \text{ divided by } 18) * 100$	If one item is missing $([\text{Sum}(\text{the two completed items}) - 1] \text{ divided by } 17) * 100$

USA

		items – 2] divided by 12) * 100
Convenience	([Sum(Item 4 to Item 6) – 3] divided by 18) * 100	If one item is missing ([Sum(the two completed items)) – 2] divided by 12) * 100

Descriptive statistics per subscale will be provided to summarize treatment satisfaction. Patients' treatment satisfaction score will also be listed.

5.6 Medical and Surgical History

The study participant's medical history related to the following will be collected at enrollment visits:

- GI disorders
- Cardiovascular disorders
- Infections/inflammatory diseases
- Metabolic, endocrine, and bone health
- Mental health
- Social history
- Malignancies
- Surgical, radiological, and endoscopic procedures
- Laboratory abnormalities, if available/ordered as part of routine clinical practice

The frequencies and percentages of patients with reported medical and surgical history will be presented by term alphabetically. Medical and surgical history will also be listed.

Laboratory abnormalities include but not limit to

- Fecal elastase-1 test <200 mcg/g
- Iron deficiency anemia <12 ng/mL
- Megaloblastic anemia: hemoglobin <13 g/dL in men and <12 g/dL in women

USA

- Pancytopenia: Red blood cell: <4.2 million cells/cc in women / <4.7 million cells/cc in men and White blood cell: <4,000 cells/cc and Platelet: <150,000 cells/cc
- Pre-albumin <16 mg/dL
- Albumin <35 g/L or >52 g/L
- AST > 3x NL
- ALT > 3x NL
- Total bilirubin > 1.2 mg/dL
- ALP > 3x NL
- Triglycerides >300 mg/dL fasting, or >500 mg/dL non-fasting
- Elevated lipase
- Elevated amylase
- Serum lipids >200 mg/dL
- Total calcium >12.0 mg/dL
- Vitamin B12 ,160 pg/ml (118 pmol/L)
- Vitamin A <28 µg/dL
- 25-Hydroxyvitamin D <20 ng/ml
- Vitamin E <4 mg/L
- Elevated INR
- Selenium <40 ng/mL
- Zinc <70 µg/dL
- Folate <2 ng/mL
- Iron <60 µg/dL in men and <35 µg/dL in menstruating women
- Hydrogen breath test/duodenal aspirates >100,000 cfu/mL
- Elevated high-sensitivity C-reactive protein (hs-CRP) >3.0 mg/dL
- Oral glucose tolerance test (OGTT) >200 mg/dL
- Serum lipids and triglycerides >500 mg/dL or above (5.7 mmol/L or above)
- Other laboratory abnormality

USA

The age started at alcohol, tobacco, cannabis, opioids or substance abuse, and frequencies, if any, will be descriptively summarized.

5.7 Adverse Events/Serious Adverse Events

An AE is defined as any untoward medical occurrence in a study participant administered a pharmaceutical product and which does not necessarily have to have a causal relationship with the treatment. AE data collection begins after a study participant has completed an Enrollment Visit. During the Follow-Up on-site visits, the Investigator and/or designee is required to question the study participant regarding the occurrence of AEs since the previous registry visit. Pertinent details regarding any reported AEs are to be captured using the pertinent sections in the Investigator Follow-Up forms.

Any AEs that are reported by the study participant, discovered as a result of general questioning by the Investigator, should be recorded in the Investigator Follow-Up Form at the next scheduled registry visit following the onset of the event.

At the Follow-Up Visits, Investigators will provide information on any AEs/SAEs that may have occurred since last visit. For every AE that is reported, the following information will be collected:

- Event term
- Onset date
- Relation to PERT
- Event seriousness
- Any other events meeting SAE definition
- Outcome of SAE

SAEs are defined as adverse events that result in any of the following outcomes:

- Hospitalization (new or prolongation)
- Death

USA

- Immediately life threatening (urgent intervention required to prevent outcome of death)
- Persistent/significant disability or incapacity
- Congenital abnormality or birth defect
- Otherwise serious (important medical event) in the opinion of the Investigator (i.e., event that may jeopardize the study participant and require medical or surgical intervention/treatment to prevent one of the other outcomes listed above)

For any reported SAE, the following information will be collected:

- SAE event term
- SAE onset date
- SAE outcome (i.e., hospitalization, immediately life-threatening, death, persistent/significant disability, congenital abnormality or birth defect, treatment with intravenous antibiotics or anti-infectives, otherwise serious in the option of the Investigator)
- SAE final outcome/status (i.e., resolved/fully recovered, recovered with sequelae, ongoing, death, condition worsening)
- Brief description of the study participant with no personal identifying information
- Intervention/treatment for the SAE (i.e., medication or nutritional supplement, device, surgery, behavioral/lifestyle, observation)
- Details on medications used for the disease under study (i.e., drug name, dose, frequency, route, start date, date of last dose, event relation to the drug, continuation/discontinuation/changes of the drug)
- List of any relevant tests, laboratory data/results, and history, including preexisting conditions
- Brief description/narrative of the SAE
- Status of the SAE report (i.e., confirmed event, SAE previously reported between registry visits/duplicate, not an event)

Severity and causality of all AEs are determined by the Investigators.

USA

An overall summary of the incidence of AEs/SAEs (number of patients with any events and number of events, if applicable) will include the following:

- All AEs
- All SAEs
- PERT- suspected to be related AEs
- SAEs leading to study discontinuation
- SAEs leading to dose interrupted
- AEs leading to death

AEs (number of patients with any events and the number of patients with specific AEs/SAEs arranged alphabetically by term will be tabulated for the following:

- AEs
- SAEs
- PERT- suspected to be related AEs
- SAEs leading to study discontinuation
- SAEs leading to dose interrupted
- AEs leading to death

When a patient has the same adverse event reported multiple times, the patient will only be counted once in adverse event frequency tables.

All AEs, SAEs and deaths will be listed.

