7.2 Medical History and AEs

At Enrollment, the Investigator will provide information on the study participant's medical history related to the following:

- GI disorders
- Cardiovascular disorders
- Infections/inflammatory diseases

- Metabolic, endocrine, and bone health
- Mental health
- Social history
- Malignancies
- Surgical, radiological, and endoscopic procedures
- Laboratory abnormalities, if available/ordered as part of routine clinical practice

At the Follow-Up Visits, Investigators will provide information on any AEs/SAEs that may have occurred since last visit. For every AE that is reported, the following information will be collected:

- Event term
- Onset date
- Relation to PERT
- Event seriousness
- Any other events meeting SAE definition
- Outcome of SAE.

For any reported SAE, the following information will be collected:

- SAE event term
- SAE onset date
- SAE outcome (i.e., hospitalization, immediately life-threatening, death, persistent/significant disability, congenital abnormality or birth defect, treatment with intravenous antibiotics or anti-infectives, otherwise serious in the option of the Investigator)
- SAE final outcome/status (i.e., resolved/fully recovered, recovered with sequelae, ongoing, death, condition worsening)
- Brief description of the study participant with no personal identifying information
- Intervention/treatment for the SAE (i.e., medication or nutritional supplement, device, surgery, behavioral/lifestyle, observation)
- Details on medications used for the disease under study (i.e., drug name, dose, frequency, route, start date, date of last dose, event relation to the drug, continuation/discontinuation/changes of the drug)
- List of any relevant tests, laboratory data/results, and history, including preexisting conditions
- Brief description/narrative of the SAE
- Status of the SAE report (i.e., confirmed event, SAE previously reported between registry visits/duplicate, not an event)

At each Follow-up, Investigators will also complete a COVID-19 reporting form, which will collect the following information:

- COVID-19 diagnosis

- COVID-19 symptoms (i.e., fever or chills, cough, shortness of breath or difficulty breathing, fatigue, muscle or body aches, headache, new loss of taste or smell, sore throat, congestion or runny nose, nausea or vomiting, diarrhea)
- COVID-19 vaccination date(s) and manufacturer(s), if applicable

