Appendix B – Study Participant Exit Form

What is the reason for the study participant's exit?

- Study participant withdrew from the study
- Study participant was terminated by the Investigator
 - Please specify reason: **[ADD FREE TEXT]**
- Study participant is lost to follow up
- Study participant transferred care to another gastroenterologist
- Data collection period of the registry has ended

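### SAP 5.7 tabulates SAEs leading to study discontinuation without a coded source and SAEs leading to dose interruption without a derivation, while SAEs with PERT discontinued and PERT-related SAEs have no row of their own

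*SAP*

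**What the plan says.** SAP 5.7 plans the same six categories twice, in an overall summary and in tables by event term: all AEs, all SAEs, "PERT- suspected to be related AEs", "SAEs leading to study discontinuation", "SAEs leading to dose interrupted", and AEs leading to death. It also lists every AE, SAE and death individually.

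The items collected are set out in Protocol 7.2 and repeated in SAP 5.7. Every AE carries its relation to PERT and its seriousness. Every SAE also carries details of the medications used for the disease under study. These are "drug name, dose, frequency, route, start date, date of last dose", followed by "event relation to the drug, continuation/discontinuation/changes of the drug". The protocol describes the drug action in the same words: "continuation/discontinuation/changes of the drug".

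Study exit is recorded separately. The Exit Form in Protocol Appendix B has five options. One of them, "Study participant was terminated by the Investigator", asks for a free-text reason; the other four do not. Protocol section 10 says that the form is where reasons for withdrawal are given. Protocol 6.4 adds death as an exit reason and asks for associated AEs in that case.

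**The concern.** In this registry, leaving the study and stopping the drug are different events. PERT is required at enrollment, but stopping it is not among the exit reasons in Protocol 6.4 or the Table 1 footnote. A participant who stops PERT at an SAE therefore stays in follow-up and does not count in a row defined by study exit. The drug action for that same SAE is collected and reaches no table row.

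The protocol background gives the study of effectiveness and safety of available therapies as a reason why registries are needed. If the only discontinuation row has no coded source, a low count reflects missing linkage as much as missing events. The table would not tell the reader which. For dose interruption, two programmers working from the same SAP could reach different counts.

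**Working it through.** There is no figure in the plan to reproduce, and no arithmetic decides the point. The check maps table rows to listed items, and then listed items back to rows.

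**Inputs.** Six table categories (SAP 5.7); six AE items and ten SAE items (Protocol 7.2, SAP 5.7); five Exit Form options (Protocol Appendix B); six exit reasons (Protocol 6.4); the disposition categories (SAP 5.2).

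**Rows to items**

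| Row in SAP 5.7 | Listed source |
|---|---|
| AEs | AE event term |
| SAEs | Event seriousness, SAE form |
| PERT-related AEs | Relation to PERT |
| AEs leading to death | SAE outcome includes death |
| SAEs leading to study discontinuation | No coded item |
| SAEs leading to dose interruption | Drug-action item exists, but no rule |

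Four of the six rows have a listed source. The other two need a closer look.

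1. *Study discontinuation.* None of the 6 + 10 = 16 AE and SAE items records that an event led to exit. None of the five Exit Form options is an adverse event. SAP 5.2 has no such disposition category either, only a residual one for other reasons. What remains is partial and uncoded:
   - deaths, which already have their own row;
   - free text for investigator termination;
   - the SAE narrative;
   - withdrawal reasons, which section 10 expects but for which Appendix B shows no field.

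   Exits by loss to follow-up or transfer carry no reason that could name an SAE. The SAP gives no rule for reading any of these sources.

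2. *Dose interruption.* The listed levels of drug action are continuation, discontinuation and changes. An interruption could be entered as a change or as a discontinuation. The SAP does not say which, and it does not separate a temporary stop from a permanent one, a dose increase or a brand switch.

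**Items to rows**

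3. *PERT discontinued at an SAE.* This can be derived from drug name and drug action on the SAE form. It has no row. Nor does another planned table show it: the reasons for switching PERT in SAP 5.5 have no safety category, and someone who simply stops could surface only under the noncompliance rule in that section.

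4. *SAEs suspected related to PERT.* These can be derived as relation to PERT crossed with seriousness. They are counted only inside the row for all PERT-related AEs, where serious and non-serious events are pooled.

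**Result.** Two of six rows have no defined source or derivation, two derivable categories have no row of their own, and this holds in both sets of tables.

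**The case against.** The strongest reply is that little is lost. All SAEs are listed, and PERT-related SAEs are already counted within PERT-related AEs. Safety is not one of the six specific aims, and the tables are purely descriptive. The full case report forms and table shells are not part of the documents. Appendix B omits death although Protocol 6.4 names it, so the form shown may be incomplete. All of this stands, and it limits the claim to items listed in the protocol and SAP. It does not remove the gap, because a listing is not a summary row and the SAP has to say how each row is filled.

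A reader might infer more in five places, and the documents do not support it.

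- *No form records dose interruption.* The drug-action item, with dose and date of last dose, may hold it. What is missing is a rule.
- *PERT-related SAEs are absent from the tables.* They are included; only the serious subset is not shown separately.
- *The study-discontinuation row would be empty.* Deaths, free text, narratives and any recorded withdrawal reasons can feed it.
- *The damage can be quantified by assuming a rate of PERT stopping and comparing it with a confidence limit for an empty row.* Those are two different quantities. A limit for study exits says nothing about PERT stopping, and SAP 5.7 plans no interval for these rows.
- *The form records that an SAE caused PERT to be stopped.* It lists the drug's status and the event's relation to the drug, not the reason for stopping. A new row should therefore be labelled as SAEs with PERT discontinued, not as SAEs leading to it.

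SAP 5.7 also states: "Severity and causality of all AEs are determined by the Investigators". Severity is not among the listed AE items. That is a real but minor mismatch, and no planned table depends on it.

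**Conclusion.** The point holds in a limited form. The study-discontinuation row would tend to undercount, since an exit by withdrawal, loss to follow-up or transfer that follows an SAE has no coded link to it. By its definition, the row also misses participants who stop PERT at an SAE and remain in the registry. The dose-interruption row is ambiguous rather than unsupported. SAEs with PERT discontinued and SAEs suspected related to PERT are derivable and deserve rows.

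The size is two of six categories, in both the overall and by-term tables. How many participants are affected cannot be stated, because the documents give neither SAE nor PERT-discontinuation rates. The conclusion assumes that the item lists in the protocol and SAP, and the Exit Form as printed, reflect what is collected. A coded SAE reason on the actual exit form, or a rule in the shells, would resolve the corresponding part.

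**What to change.** In SAP 5.7, for both the overall summary and the by-term tables:

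- Add a row for SAEs with PERT discontinued, taken from the SAE form's drug-action item for PERT products.
- Add a row for SAEs suspected related to PERT, from relation to PERT crossed with seriousness. Relation is also recorded on the SAE form, so name which item is the source.
- Define dose interruption from the drug-action item and the date of last dose. Do not equate it with every recorded change, which could include dose increases or brand switches.
- Keep the study-discontinuation row only if an AE/SAE reason is added to the Exit Form. Otherwise drop it.

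The two new rows use data already listed for collection. The cost is SAP and shell wording, plus one Exit Form option if the study-discontinuation row is kept. Exits documented before that option is added would still lack a coded reason, and a table footnote should say so.

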3.2 Study Duration

This is a 5-year study with an anticipated first enrollment date of 01 April 2021. The total enrollment period will be 24 months in length and data collection and study close-out will take place 3 months prior to the anticipated study end date. The study duration from enrollment to study end is five (5) years.

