6. STUDY PROCEDURES

6.1 Schedule of Assessments

The registry activities are summarized in the schedule of assessments outlined in **Table 1**.

Table 1. Schedule of Assessments

	Enrollment Day 0	Follow-up direct from study participant ± 7 days		Follow-up on-site (Clinical encounter)	Study participant exit [‡] May occur any time; max. data collection period is 5 years
		Every 3 months	Every 6 months		
Study Participant Provided Data[§]					
Informed consent	X				
Demographic information	X				
Family disease history	X				
Training for remote assessment completion	X				
Height	X				
Weight	X	X			
Current Insurance/work status	X	X			
Current OTC nutritional/herbal supplements	X	X			
Abdominal pain	X	X			
GI symptoms	X	X			
PERT use and treatment satisfaction	X	X			
Dietary habits	X		X		
Health-related quality of life	X		X		
Anxiety/depression	X		X		
Healthcare utilization	X		X		
Investigator Provided Data[*]					
Review/confirm participant eligibility	X				
EPI diagnosis	X				
CP etiology	X				
Medical history	X				
EPI clinical manifestations	X			X	
AEs [•]				X	
Current treatment(s)	X			X	
Reason for exit					X

[§] Study participant provided data will be collected remotely via EDC portal.

^{*} Investigator provided data will be provided during clinical encounters at the registry site. Every 180 days ±30 days with minimum 150 days between visits unless follow-up visit meets criteria for EARLY On-Site Follow-Up (see section 6.3.2)

[‡] Occurs if data collection period has ended or if study participant exits the study due to death, is LTFU, transfers to another gastroenterologist, withdraws from the study or being terminated by the Investigator.

[•] The Investigator will provide information about the occurrence and seriousness of AEs at Follow-up. In the event that an AE is serious, the Investigator will complete an SAE form.

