3 STUDY DESIGN

3.1 Overall Design

This is a prospective, non-interventional study for individuals with EPI due to CP who are under the care of a gastroenterologist. Longitudinal data will be collected from both study participants as well as from their clinical encounters with their treating gastroenterology providers using a structured and standardized data collection method. The scope of data collection (see [Table 1](#)) from the study participants includes demographics, current work status, current insurance coverage, family disease history, weight/height, current over the counter (OTC) herbal/nutritional supplements, healthcare utilization, and PROs on abdominal pain, GI symptoms, dietary habits, health-related quality of life, depression/anxiety, and PERT use and treatment satisfaction. At the time of routine clinical encounters, Investigators complete assessments on medical history, information on suspected/confirmed EPI diagnosis, CP etiology, clinical manifestations of EPI (GI and nutritional manifestations), AEs, and current treatment(s).

This is a 5-year study with an anticipated first enrollment date of 01 April 2021. The total enrollment period will be 24 months in length and data collection and study close-out will take place 3 months prior to the anticipated study end date. The study duration from enrollment to study end is five (5) years.

Study data will be collected from Investigators at the time of routine clinical encounters, as well as from study participants remotely in between routine visits.

Enrollment

Study participants will be enrolled in the study if they meet eligibility criteria and after they have provided consent to participate. During the Enrollment Visit, the Investigator will confirm eligibility and will provide information on suspected/confirmed EPI diagnosis (date of diagnosis, date of onset of symptoms indicative of EPI, method of EPI diagnosis, if applicable), CP etiology, clinical manifestations of EPI (i.e., GI and nutritional manifestations), medical history (comorbidities, surgical and radiological procedures, endoscopic procedures, and laboratory abnormalities), and current treatment(s). Information collected from the study participant

USA

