includes demographics, current work status, current insurance coverage, family disease history, weight/height, current over the counter (OTC) herbal/nutritional supplements, healthcare utilization, and participant-reported outcome assessments on abdominal pain, GI symptoms, health-related quality of life, depression/anxiety, and PERT use and treatment satisfaction.

Follow-Up

Follow-up data will be collected from the study participants remotely via electronic data capture (EDC) portal. Every 3 months, study participants will complete assessments on current work status, current insurance coverage, current weight, current OTC herbal/nutritional supplements, and abdominal pain, GI symptoms, and PERT use and treatment satisfaction. Every 6 months, in addition to the assessments completed every 3 months, study participants will also complete assessments on health-related quality of life, depression/anxiety, and healthcare utilization.

The Investigator will provide updates during routine clinical encounters approximately every 6 months or at least 150 days from the last registry visits. Data will be collected on clinical manifestations of EPI, current treatment(s), and active assessment of adverse events/serious adverse events (AEs/SAEs) since last visit. “Early” follow-up visits will be conducted whenever a study participant is prescribed a new PERT product. The Investigator will not complete any assessments if the study participants do not return to the sites for their expected routine clinical encounter.

Study Participant Exit

Study participants exit the study upon withdrawal from the study, lost to follow-up (LT FU), transfer of care to a different gastroenterologist, death, or any other reason resulting in a study participant’s exit. The Investigator will document the reason for the exit.

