5 STATISTICAL CONSIDERATIONS AND ANALYSES

5.1 General Considerations

All statistical procedures will be completed using SAS® version 9.4 or higher.

Continuous variables will be summarized using descriptive statistics, including the number of patients with non-missing value (n), mean, median, standard deviation (SD), minimum and maximum. “n” will be presented without a decimal point, minimum and maximum values will be presented with the same precision as in the database, mean and median will be presented with one more decimal place than the minimum and maximum, and SD will be presented with one more decimal place than the mean and median.

For categorical variables, summaries will include counts of patients (frequencies) and percentages. Percentages will be rounded to one decimal place. Descriptive summaries of change from baseline in categorical variables will be provided using shift tables, if applicable.

Day 0 is defined as the date when patients sign ICF.

No data imputation for any missing data will be done in this study.

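### The AE and SAE tables report participants with events without person-time or a time horizon, although planned follow-up ranges from about 33 to 57 months

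*SAP*

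**What the plan says.** SAP 5.7 plans an overall incidence summary of AEs and SAEs, given as "number of patients with any events and number of events, if applicable". It then plans tables of participants with each event, by term. For an event reported repeatedly in one participant, "the patient will only be counted once in adverse event frequency tables". All AEs, SAEs and deaths are also listed. The section names no denominator, person-time, rate or cumulative incidence. Percentages enter through the general rule in SAP 5.1: "For categorical variables, summaries will include counts of patients (frequencies) and percentages". SAP 5.2 summarises completion and reasons for exit but not length of follow-up.

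The calendar is in Protocol 3.2 and SAP 3.1. On duration: "The study duration from enrollment to study end is five (5) years". On accrual: "The total enrollment period will be 24 months in length". On closing: "data collection and study close-out will take place 3 months prior to the anticipated study end date". Table 1 in Protocol 6.1 says instead that the "max. data collection period is 5 years".

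On AE capture, SAP 3.1 states: "The Investigator will not complete any assessments if the study participants do not return to the sites for their expected routine clinical encounter". The protocol has other routes. SAEs are reported within one business day of site awareness, whether or not a registry visit takes place (Synopsis, Data Collection; 9.2). AEs on participant forms are transcribed to the Investigator Form (8.3). A later visit covers the period since the last registry visit (6.3.2). When exit is by death, AEs after the last visit are recorded (6.4).

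**The concern.** A percentage of participants with an event has a clear meaning when everyone is observed for the same time. Here they are not. The last participants enrolled can be followed for little more than half as long as the first, even if nobody leaves. Withdrawal, transfer of care, termination, death and loss to follow-up shorten observation further. Loss to follow-up follows two consecutive missed remote assessments (Protocol 6.4). These fall every 3 months, so it can occur from about 3 + 3 = 6 months.

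The reported percentage then reflects accrual pace and retention as well as event risk. Because follow-up time is not summarised either, a reader could not recover the exposure behind it. The protocol's Background gives the study of the safety of available therapies as one reason why registries are needed, and a percentage with no time base serves that purpose poorly. Protocol section 11 foresees rates with 95% confidence intervals for healthcare utilization, but there is no equivalent for AEs.

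**Working it through.** The plan states no AE rate, exit rate or expected percentage, so there is no figure of its own to reproduce.

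**Step 1: planned follow-up.** Inputs from Protocol 3.2: duration 60 months, enrollment 24 months, close-out 3 months before the end.
- First enrolled: 60 − 3 = 57 months.
- Last enrolled: 60 − 3 − 24 = 33 months.
- Ratio 57/33 = 1.73; mean 45 months under uniform accrual.
- If Table 1's five-year maximum is read without the close-out: 60 and 60 − 24 = 36 months, ratio 1.67.

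**Step 2: the pooled crude percentage.** Assumptions, none from the documents: constant first-event hazard λ, uniform accrual, and exit with constant hazard d that is independent of AEs. With annual exit proportion a, d = −ln(1 − a)/12 per month. Let h = λ + d, and let m be the mean of exp(−ht) over t from 33 to 57:

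m = [exp(−33h) − exp(−57h)] / (24h)

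Crude proportion = (λ/h)(1 − m). Person-years at risk for N = 400 are (400/12)(1 − m)/h. True risk at t months is 1 − exp(−λt).

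Take 5 first events per 100 person-years: λ = 0.05/12 = 0.004167 per month.
- No exit: h = 0.004167, m = 0.829, crude = 1 − 0.829 = 17.1%.
- 30% annual exit: d = 0.02972, h = 0.03389, λ/h = 0.1229, m = 0.2237, crude = 0.1229 × 0.7763 = 9.5%.

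True risk: 4.9% at 12 months, 12.8% at 33, 21.1% at 57.

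| Annual exit | Crude % | Ratio to 57-month risk | Ratio to 33-month risk | Ratio to 12-month risk | Participants with event / person-years | Rate per 100 person-years |
|---|---|---|---|---|---|---|
| 0% | 17.1 | 0.81 | 1.33 | 3.50 | 68/1365 | 5.0 |
| 10% | 14.1 | 0.67 | 1.10 | 2.90 | 57/1131 | 5.0 |
| 20% | 11.7 | 0.55 | 0.91 | 2.39 | 47/932 | 5.0 |
| 30% | 9.5 | 0.45 | 0.74 | 1.96 | 38/764 | 5.0 |

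The rate stays at 5.0 because the model has a constant hazard and independent exit. The crude figure moves although the risk does not.

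**Step 3: sensitivity.** For assumed rates of 2 to 20 per 100 person-years and annual exit of 0% to 30%, the ratio of crude figure to 57-month risk runs from 0.44 to 0.86. With follow-up of 36 to 60 months (the same formula with those limits) at 5 per 100 person-years:
- No exit: m = 0.819, crude = 18.1%.
- 30% exit: m = 0.202, crude = 0.1229 × 0.798 = 9.8%.

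The conclusion does not depend on which calendar reading applies.

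**The case against.** The case for leaving the plan alone is that this is a single-cohort descriptive registry. None of the six aims is a safety aim, AEs are not among the dependent variables in SAP 5.15, and no AE comparison between products or sites is planned. Counting a participant once per term is standard, event counts (if applicable) and full listings are planned, and the table templates, in a separate document not available here, may state a denominator. All of this is fair. It limits the consequence to interpretation; no test or decision depends on these tables. It does not supply a time base, because neither event counts nor listings are a person-time summary.

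Two stronger readings are tempting and the documents do not support them.

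- *AEs are captured only when participants return, so those who stop attending count as event-free.* SAEs are reported on site awareness regardless of visits, participant-form AEs are transcribed, late visits look back, and AEs after the last visit are recorded at exit by death. Events before a participant stops attending still count. What remains is possible under-capture of non-serious AEs in participants who never return.
- *The percentages simply understate risk.* That holds against the full period. Against 33 months, the illustration gives a crude figure 1.33 times the true risk with no exit and 0.74 times with 30% annual exit, so the direction depends on the horizon and on dropout.

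**Conclusion.** The point stands as a recommended change to the safety tables. Following SAP 5.7 produces percentages that belong to no defined period, in a cohort whose planned follow-up differs by a factor of about 1.7 before any early exit. In the illustration, one fixed event rate gives crude figures from 17.1% down to 9.5% according to dropout alone.

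The follow-up range rests on the documents' calendar. The percentages rest on an assumed event rate, a constant hazard, uniform accrual and exit unrelated to AEs. The documents give no AE or exit rates, so the actual size of the distortion cannot be stated. The once-per-participant rule is not itself a fault; the gap is the missing person-time measure beside it.

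**What to change.** In SAP 5.7:

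1. Keep the participant counts, event counts and listings. State the denominator and summarise follow-up time.
2. For all AEs, all SAEs and PERT-related AEs, add participants with a first event per 100 person-years at risk, with exact Poisson 95% confidence intervals. Time at risk starts when AE collection starts, after the Enrollment Visit, and stops at the first event.
3. If total-event rates are shown, use an interval that allows for repeat events within a participant (robust variance or negative binomial). A simple Poisson interval would tend to be too narrow.
4. End person-time for non-serious AEs at the last on-site visit with AE assessment. End it for SAEs and deaths at study exit or last contact, because these can be reported after that visit and would otherwise enter the numerator without matching time. State which window applies to rows that mix serious and non-serious events, and count only events with onset inside it.
5. Give cumulative incidence at 12, 24 and 33 months, with censoring at the end of observation and death as a competing event.

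The cost is SAP wording and a few table columns. AE and SAE onset dates are collected under SAP 5.7 and the exit date under SAP 5.2. Tables become slightly longer. Rates do not remove bias from informative dropout, and the SAP should say so.
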